8.3 Statistical methods

Outcome Measures and Covariates

Primary outcome: The primary outcome will be a binary indicator of whether or not the patient is retained on MAT (methadone, buprenorphine, or buprenorphine-naloxone) treatment through 24 weeks. For those who drop out before 24 weeks, time (week) of dropout will be recorded, and they will be considered as not retained.

Secondary outcomes: 1) weeks of treatment retention (time to drop-out 0-24 weeks, survival; number of weeks retained, continuous); 2) urine-confirmed abstinence from opioids in the last 4 weeks (longitudinal (weeks 4, 8, 12, and 24), binary); 3) Days using opioids in the last 4 weeks (longitudinal, continuous); 4) Days using other drugs/alcohol in last 4 weeks (longitudinal, continuous); 5) coping strategies (CSS mean score; longitudinal, continuous); 6) social functioning (EuroQol, SCS, global scores and subscales; longitudinal, continuous); 6) overall mental health symptoms (K10; longitudinal, continuous); 7) HIV risk behavior—days in past 30 of vaginal or anal sex without a condom (longitudinal, continuous); Any needle sharing in past 4 weeks (longitudinal, binary); 7) Treatment satisfaction at week 24 (IAFF; continuous); 8) Serious adverse events (binary).

Additional variables: *Covariates, primary and secondary analyses:* Stratification factors: 1) any intravenous drug use (binary); 2) treatment with methadone vs buprenorphine at Hub vs buprenorphine at Spoke (categorical). *Moderators:* 1) both stratification factors will be explored as moderators; 2) demographic characteristics (gender, age, ethnicity etc.); 3) prescription opioid use only vs any heroin or fentanyl use (binary); 4) other substance use at baseline (any cannabis, any stimulant, any heavy drinking days; binary); 5) Probable major depression at baseline (binary based on PHQ score); 6) history of prior treatment for opioid use versus first treatment episode (binary). *Mediators:* 1) social functioning (EuroQol; continuous); 2) social connectedness (SCS; continuous); 3) opioid craving (continuous); 4) coping (CSS; continuous); and 5) mental health symptoms (K10; continuous).

Intent to Treat, Dropouts, and Missing Data

All analyses will be on the Intent-to-treat (ITT) sample, i.e., all randomized subjects (N=200) according to the treatment arm to which they were assigned. For the primary outcome, patients that dropped out before 24 weeks will be considered not retained. For the secondary outcome urine-confirmed abstinence, missing data (patients who cannot be located) will assumed to be opioid positive (not abstinent), a typical assumption which is reasonable based on the high rate of relapse among patients with OUD who discontinue medication treatment (Weiss et al., 2011; 2015; Hser et al., 2016; 2017). For other secondary outcomes, missing data will be treated as missing at random. Longitudinal mixed effects models do not require complete data to provide estimates of the outcome, and the estimates are considered valid under the assumption that the data are missing at random (Little & Rubin, 2002). We will additionally perform sensitivity analysis for the secondary outcomes to examine the influence on the outcomes of dropout and missing data by performing several imputation methods, for instance imputing missing weeks as all abstinent or all non-abstinent. Comparison of the inferences from assuming various models for the missingness provides a measure of the validity of the efficacy estimate from the initial model.

Significance Testing and Preliminary Analyses

All tests for main effects will be performed at two-sided significance level of 5%. Before performing specific analyses, we will examine the distribution of outcome measures and covariates and investigate for outliers. The distributions of continuous variables will be checked for normality, and transformed, if necessary. Distribution of demographic variables will be examined and described in terms of means, standard deviations, proportions and 95% confidence intervals. Covariates will be examined for association with treatment outcome. Covariates associated with treatment outcome will be adjusted for in models used to test study hypotheses.

Primary outcome

Statistical Model: *Hypothesis: Adding reSET-O to TAU (reSET-O + TAU arm) will promote greater 24 week retention in treatment on buprenorphine compared to the TAU arm.* The positive effect of randomization to the reSET-O+TAU group compared to TAU group will be estimated using logistic regression with the binary outcome of retention in treatment for 24 weeks (yes/no) modeled as a function of treatment condition (reSET-O + TAU vs TAU) and stratification factors (methadone treatment; buprenorphine treatment at Hub; buprenorphine treatment initiation at hub and continuation at spoke) and intravenous drug use in last 30 days (yes/no). The odds ratio of the treatment term and its confidence limits will estimate the treatment effect. The raw retention rates in each treatment group and rate differences will be computed for descriptive purposes.

Secondary outcomes

Statistical Models: For each of the secondary outcomes (see above) the effect of randomization to the reSET-O+TAU arm compared to the TAU arm will be estimated with a model of the same general form as for the primary outcome (three independent variables: treatment assignments (reSET-O+TAU vs TAU) and the two stratification factors) using logistic regression model (for binary outcomes), generalized linear model (for continuous outcomes), or longitudinal generalized mixed effects model (for longitudinal outcomes) with appropriate link functions (e.g. logit for binary outcomes). Longitudinal outcomes analyzed using a mixed effects models will utilize a generalized estimating equation with an autoregressive correlation structure to account for within subject correlation over time, as well a random intercept accounting for between subject variability. Retention data will be displayed with Kaplan-Meier curves that show the observed probability of retention in the program until time t, over time across the 24-week trial. The time to not-retained (dropout) data for reSET-O +TAU and TAU groups will be analyzed using proportional hazards models with covariates. If proportional hazard assumption is not satisfied, the data will be analyzed using a non-parametric log-rank test. In addition to stratification factors, covariates that are found to be related to the outcomes will be also added to the models to improve the power for detecting significant differences.

Moderation and Mediation

Moderation Statistical Models: The effect of randomization to the reSET-O+TAU arm will be estimated for subpopulations based on the demographic and baseline characteristics selected as moderators (see above). We will estimate the moderation effect on primary outcome using a similar model to Aim 1 primary outcome with the inclusion of moderator by treatment interaction: $Y_i = \beta_0 + \beta_1 Trx_i + \beta_2 M_i + \beta_3 Trx_i M_i + \beta_4 C_i + s_i$ where M_i is the moderator status for i^{th} subject and Trx_i is subject's treatment assignment. Regardless of the significance of the interaction term, we will use the model to estimate the 95% confidence interval of the treatment effect for each level or category of the moderator variable. The moderator analyses are exploratory and hypothesis generating, but significant moderator effects can be useful in planning future efforts at implementation of reSET-O by identifying subgroups that may particularly benefit. Identifying subgroups where there is less benefit may suggest future modifications to reSET-O or its implementation strategy to achieve better effect in those subgroups.

Mediation Statistical Models: The effect of randomization to the reSET-O +TAU arm will be estimated when accounting for potential mediators (see above). In particular, we are interested in testing whether an impact of treatment on the primary outcome of 24 week buprenorphine retention is mediated by craving and by coping skills (CSS), which are targets of the therapy lessons or modules of reSET-O, as well as social functioning (PROMIS) and social connectedness. We will simultaneously estimate both the total effect of treatment assignment on primary outcome and the indirect of treatment assignment on primary outcome mediated through the intended target mediators using structural equation modeling (SEM) in software MPlus (Taylor, MacKinnon and Tein 2008). The indirect effect is estimated by the product of the effect of treatment assignment on the mediator and the effect of the mediator on the primary outcome while adjusting for treatment assignment. SEM will provide an estimate of the indirect effect of each mediator as well as its bootstrapped 95% confidence interval. These mediational analyses explore whether the effect of reSET-O on the primary outcome is being channeled through reSET-O

having an impact on its intended targets (abstinence/relapse prevention, and psychosocial functioning) (i.e. main effects of treatment assignment on mediator). This can, again, be of heuristic value in suggesting aspects of either reSET-O itself or its implementation that might need strengthening in future research or implementation efforts.

Implementation Outcomes

Measures of reSET-O utilization and adherence (number and types of therapy lessons completed, incentives earned, utilization of communication features) will be summarized with descriptive statistics, and associations with baseline covariates explored to understand what factors may drive reSET-O utilization, including patient characteristics and clinical setting (Hub vs Spoke).

Qualitative Interviews conducted with reSET-O patients will elicit personal their experiences with reSET-O and its acceptability, feasibility, barriers and facilitators, and suggestions for improvement. A Qualitative Interview was previously developed in consultation with the Advisory Board, for the R21 pilot trial (Penn State IRB 00009931). Qualitative data analyses from the result of the qualitative interview, as well as using experiences from the R21 pilot trial and adaptation process, may indicate changes to improve the current qualitative interview that is expected to be used and incorporate standard implementation outcomes (Glasgow et al., 1999). Using Atlas.ti[®] software and a coding framework developed from the qualitative interview, research staff ([name], [name]) will systematically code transcripts of the interviews, resolving discrepancies in consensus discussion. The descriptive implementation data and interviews will be presented to the Advisory Board and used to help understand the feasibility of future implementation efforts across the State and beyond.

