- Timeline Follow-Back (TLFB) (Sobell and Sobell, 1992; 2000) assesses self-reported alcohol and other drug use (frequency, quantity) using calendars and memory aids to enhance recall. We will not be able to provide printed calendars; however, the participant will be encouraged to use their phone or tablet device to view a calendar app to help enhance their recall of past substance use. The TLFB has good psychometric properties, including test-retest reliability with multiple populations, and content, criterion, and construct validity across multiple related measures. Additional questions will assess intensity and number of days of urges/cravings for opioids and other substances, and HIV risk as a result of IV drug use and sharing of needles/works. Per the recommendation of the NIH, staff who are blinded to the randomization assignment of participants should complete the TLFB. Penn State research staff will complete the TLFB during baseline because it will be completed before randomization occurs. Columbia research staff will be completing the TLFB via phone/WebEx session with all subjects beginning with the 4-week follow-up visit. During the follow-up visits, Penn State research staff will complete all research tasks with the participants and help facilitate the TLFB with the Columbia team by:
 - Transferring the participants to the Columbia team by phone, text or email;
 - Providing a phone number or meeting room link so participants could reach out to the Columbia team directly; and/or
 - Providing the Columbia team with the participant's contact information (at the participant's request).
 - The research tasks with the Columbia team will occur through the participant's phone or an office phone via WebEx. Columbia University requires the use of WebEx for research outreach to participants.
- Coping Strategies Scale (CSS) (Litt et al., 2003) is a 23-item, self-report measure (originally adapted from the Processes of Change (Proschaska et al., 1998)), assessing change processes, coping skills, and problem-solving related to urges to use substances. It has good reliability across samples ($\alpha=.83$ to $.87$). Two versions with only slight differences in directions will be administered. At intake, the directions will ask subjects to think about the last three months

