when answering the questions. For all follow-up research appointments, the directions will ask the subject to think about their coping strategies used since the last research appointment. Question/prompt items remain the same between the two versions.

- PROMIS is a well validated and widely used scale that measures the quality of social and occupational functioning.
- Social Connectedness Scale (SCS) (Lee and Robbins 1995; 1998) is a 20 item, 6-point scale, self-report assessing psychological belonging or interpersonal closeness with good reliability ($\alpha=.91$).
- Patient Health Questionnaire (PHQ) (Spitzer et al., 1999) was developed for use in primary health settings and screens for DSM psychiatric diagnosis of major depression and generalized anxiety at baseline.
- The Kessler 10 (K10) (Kessler et al., 2003) is a brief, 10-item self-report measure of general psychiatric distress will be collected at baseline and follow up points to address change in psychiatric symptoms over time. K10 has good reliability and is used in World Health Organization mental health surveys in 30 countries.
- HIV Risk from the Sexual Experiences and Risk Behavior Assessment Schedule (SERBAS): A summary item from the Sexual Experiences and Risk Behavior Assessment Schedule (SERBAS), used as primary outcome in large HIV risk reductions studies (Tross et al., 2010), elicits the number of episodes of occasions of vaginal or anal intercourse without a condom over the last 90 days using time-line follow back cues for recall.
- Time Line Follow-Back (see above) will query intravenous drug use, and episodes of sharing needles.
- Columbia Suicide Severity Rating Scale (C-SSRS) (Posner et al., 2008):_ The C-SSRS will be administered only to subjects who have endorsed suicidal ideation (SI) per the Patient Health Questionnaire (PHQ). There is one item on the PHQ that assesses self-reported SI using a Likert scale of 0-3 (0 = not at all; 3= nearly every day). A score of 1 or higher is considered an SI endorsement, which will warrant administration of the C-SSRS. Should the C-SSRS results indicate an SI presence/plan, a Hub PPI provider (physician or nurse practitioner) will take over the evaluating situation and follow PPI's SI policy.

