- Overdose History: This assessment asks patients if they have ever overdosed on a substance and then goes into branching logic for details of the incident if they have, with questions like "when?", what substance, etc.
- First Response Opioid Survey Tool (FROST): This survey has questions for all research participants about the first time they used opioids.

7.2.2 Week 4 (+/- 2 weeks), Week 8 (+/- 2 weeks), Week 12 (+/- 2 weeks), & Week 24 (+2/- 4 weeks)

The same procedures and measures listed above will be repeated again at the Week 4 (+/- 2 weeks), 8(+/- 2 weeks), 12(+/- 2 weeks) & 24(+2/- 4 weeks) follow up visits – measured from completion of baseline questionnaires and randomization. Given the predicted scheduling challenges with this population, we plan to incorporate a 2-week window for completion of specific visits. For the last visit, we plan to allow for a +2/-4 window in the event that we need to allow for time to locate specific subjects who have been lost to follow-up.

A qualitative interview will be conducted and recorded with patients who have been assigned to TAU + reSET-O (n=100) at week 4 to gather their initial thoughts on the app and identify factors contributing to time spent on the app. Qualitative interviews will also be conducted at weeks 8 and 12 to elicit personal accounts of their experience using the program, acceptability of the program, and suggestions for improvement. The total time to administer these qualitative interviews is estimated at 20-30 minutes. The interview will be audio recorded. The audio recording will be stored on the Hershey Network server, accessible only by assigned study staff and the PI. The interview does not ask for PHI and therefore PHI is not expected to be in the recording; however, transcriptionists will be trained to remove PHI from any interviews.

reSET-O only works for 12 weeks at a time. Therefore, at week 12, subjects who have been randomly assigned to TAU + reSET-O will repeat the reSET-O enrollment process again, which includes the PSC form, for the continuation of their access to reSET-O. Information on the first enrollment form will be identical to the second enrollment form, with the exception of phone number and email in the event that this information has changed. There is no change in

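### Four secondary outcomes look back 4 weeks from visits allowed well off target, with no rule excluding pre-randomisation or already counted days; separately, CSS recall length changes from visit to visit

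*Combined protocol and SAP*

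**What the plan says.** Section 8.3 defines four secondary outcomes over a 4-week lookback:

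- "Days using opioids in the last 4 weeks (longitudinal, continuous"
- "Days using other drugs/alcohol in last 4 weeks (longitudinal, continuous"
- "urine-confirmed abstinence from opioids in the last 4 weeks (longitudinal (weeks 4, 8, 12, and 24), binary"
- "Any needle sharing in past 4 weeks (longitudinal, binary"

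Section 7.2.2 says the assessments "will be repeated again at the Week 4 (+/- 2 weeks), 8(+/- 2 weeks), 12(+/- 2 weeks) & 24(+2/- 4 weeks) follow up visits", timed from baseline and randomisation.

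Section 8.3 gives no rule for lookback days that precede randomisation or were already scored at the previous visit. It sets no denominator for days observed, and it does not say whether actual or nominal visit time enters the longitudinal models.

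The CSS works differently. Under section 7.2.1, "At intake, the directions will ask subjects to think about the last three months", while at follow-up "the directions will ask the subject to think about their coping strategies used since the last research appointment". Section 8.3 uses the CSS both as a secondary outcome and as a mediator.

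The sexual-risk item is outside this point. Section 8.3 scores it as "days in past 30 of vaginal or anal sex without a condom (longitudinal, continuous", whereas section 7.2.1 describes a 90-day period; those two passages need reconciling in their own right.

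**The concern.** A lookback that runs from the actual visit date, combined with windows as wide as half the lookback or more, means that one visit label can describe different study days in different patients.

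At week 4, an early visit brings in days on which the randomised treatment could not have acted, which pulls the estimated difference towards zero. At weeks 4, 8 and 12, closely spaced visits feed the same calendar days into the model as two repeated measures.

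The CSS has a separate problem. A coping score recalled over three months, then over about 4 weeks, then over about 12 weeks is not the same measurement at each time. Change over time, and the mediated effect built on it, then partly reflects the length of the recall period.

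**Working it through.** **Plan's own figure.** The plan gives no number for this point. Its one sample-size calculation (section 8.2: 100 per arm, 40% vs 59.7%, two-sided 5%, 80% power) reproduces: the normal approximation gives 100 per arm and power 0.800, and the odds ratio is (0.597/0.403)/(0.40/0.60) = 2.22. It concerns 24-week retention and is untouched by what follows.

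**Inputs.** The lookback L is 28 days (section 8.3). The windows (section 7.2.2), in days from randomisation, are:

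- week 4: 14 to 42
- week 8: 42 to 70
- week 12: 70 to 98
- week 24: 140 to 182

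**Pre-randomisation days.** For a visit on day t, the number is max(0, 28 − t).

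- Day 14: 28 − 14 = 14 days, or 14/28 = 50%.
- Day 28 or later: 0. No week 8, 12 or 24 visit can include any.
- Evenly spread visits over the 29 allowed days (assumption): days 14 to 27 are affected, so 14/29 = 48% of visits. The mean is (14 + 13 + … + 1)/29 = 105/29 = 3.6 days, and 3.6/28 = about 13%.

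If the true difference were d days per 28, present from day 1 and constant, the measured difference would be d × (28 − k)/28 with k pre-randomisation days. That is d/2 at the day-14 edge, about 0.87d at the even-spread mean, and d when every visit is on time or late.

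**Days counted twice.** For two visits s days apart, the overlap is max(0, 28 − s).

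- On-time visits at weeks 4, 8 and 12: s = 28, overlap 0.
- Visits on days 42 and 49: 28 − 7 = 21 days, or 75%.
- The windows touch at days 42 and 70, so s runs from 0 to 56 and the overlap from 28 to 0. With independent, evenly spread visits (assumption), 48% of adjacent pairs overlap, by 4.8 days on average over all pairs.
- Weeks 12 and 24: the smallest s is 140 − 98 = 42, so there is never an overlap.

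**Week 24.** A visit on day 140 scores days 113 to 140; one on day 182 scores days 155 to 182. The two share no day.

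**CSS recall length.**

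| Visit | On target | Range, all visits attended |
|---|---|---|
| Intake | three months | fixed |
| Week 4 | 28 days | 14 to 42 |
| Week 8, week 12 | 28 days | 0 to 56 |
| Week 24 | 168 − 84 = 84 days | 140 − 98 = 42 to 182 − 70 = 112 |

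At week 24 that is 6 to 16 weeks with full attendance. It rises to 182 days, or 26 weeks, if every earlier follow-up was missed.

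**The case against.** The strongest reply is that these are edge cases in secondary outcomes. The 50% figure needs a visit on exactly day 14, contamination stops at day 28, and the windows are the same in both arms. This stands as to size, which is why the even-spread figure and the zero case are shown beside the edge. It does not supply the missing rule, and section 7.2.2 itself justifies the windows by expected scheduling difficulty, so off-target visits are foreseen.

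A second reply is that section 8.3 already models within-subject correlation with an autoregressive structure and a random intercept, so adjacent visits are not treated as independent. That is correct. But a correlation structure indexed by visit does not remove days that enter twice, and the amount shared differs from patient to patient.

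Several stronger readings are tempting, and the documents do not support them:

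- **Weeks 13 to 20 are lost because visits run off target.** With on-time visits, those weeks fall outside the scored periods because the visits are 12 weeks apart and the outcome is defined as the last 4 weeks at each visit. That is limited coverage by design. Section 7.2.1 also states no recall period for the Timeline Follow-Back (TLFB), so one cannot conclude that those weeks are never asked about.
- **Treatment comparisons are biased.** Rewards and a paid interview exist only in the app arm (section 13.0), so one might expect visit timing to differ by arm. No document shows that it does.
- **The CSS shares the faults of the 4-week outcomes.** Recall since the last appointment includes no pre-randomisation days, counts none twice and leaves no gap. Its fault is unequal length.
- **CSS recall can vary from 2 to 24 weeks at one visit.** The 2-week minimum belongs to week 4 and the longest periods to week 24; no single nominal visit has that range.

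**Conclusion.** The point holds as a modest improvement that should be made. Followed as written, the plan can score up to 14 of 28 pre-randomisation days at week 4 and the same days at two successive visits. The even-spread figures of about 13% on average and 48% of week 4 visits rest on an assumption about visit timing; depending on the actual dates, the share of pre-randomisation days can lie anywhere from 0% to 50%. The dilution figures further assume an immediate, constant effect.

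The reading that the lookback runs from the actual visit date is the natural one for a last-4-weeks item, and no text says otherwise. The expected consequence is dilution at week 4 and repeated measures that share days. Bias between arms would require visit timing to differ by arm.

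The unequal CSS recall follows directly from the two sets of directions and the visit schedule, and needs no assumption about off-target visits. How far it shifts CSS scores cannot be judged from the documents.

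The primary retention endpoint and N = 200 are unaffected.

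**What to change.** 1. **TLFB day counts (opioids; other drugs and alcohol).** Keep the 28-day lookback, but score only days after randomisation and after the last day already scored at an earlier visit. Analyse days used out of days observed, as a proportion or with an offset. Prespecify a minimum number of observed days, since two visits on a shared window boundary leave none for the second. Use actual visit day as time in the model.
2. **Abstinence and needle sharing.** Exclude pre-randomisation days and adjust for the number of days covered. Keep each urine with its nominal visit, so that an observed result is never treated as missing and scored opioid-positive under the section 8.3 rule. This step does not remove days shared by two visits; for these binary outcomes that is left to the within-subject correlation.
3. **CSS.** Use one recall period, the past 4 weeks, at every visit including baseline.

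The cost is a scoring rule and a change to the CSS directions, with no added visit or staff. Fewer days will be scored at early or closely spaced visits, so those scores are less precise. If enrolment has begun, the CSS change creates two versions, and the version used should be recorded for each assessment.

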8.2 Sample size determination

Previous studies of MAT treatment of OUD indicate substantial drop out rates--typically in the 40% to 50% range still retained in treatment at 24 weeks. Assuming 40% retention in the TAU treatment group, a sample size of 100 patients per treatment group (total N = 200) is selected to ensure sufficient power of 80% with a two-sided level of significance of 5% to be able to detect a difference of at least 19.7% between the TAU vs reSET-O + TAU treatment groups (i.e., 40% retained in TAU vs 59.7% retained in reSET-O + TAU). This difference of 19.7% is equivalent to an odds-ratio of 2.22 and would be clinically meaningful.

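### Baseline depression is tested as a moderator only as a yes/no split of the PHQ score, with no stated cut-point; the collected score should be tested as well

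*Combined protocol and SAP*

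**What the plan says.** Section 8.3 (Additional variables) lists among the moderators "Probable major depression at baseline (binary based on PHQ score" and "other substance use at baseline (any cannabis, any stimulant, any heavy drinking days; binary". Both rest on graded baseline instruments described in Section 7.2.1. The PHQ "screens for DSM psychiatric diagnosis of major depression and generalized anxiety at baseline", and the Timeline Follow-Back "assesses self-reported alcohol and other drug use (frequency, quantity".

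The moderation paragraph of Section 8.3 fits a "similar model to Aim 1 primary outcome with the inclusion of moderator by treatment interaction". Whether or not the interaction is significant, it will "estimate the 95% confidence interval of the treatment effect for each level or category of the moderator variable". It also states: "The moderator analyses are exploratory and hypothesis generating".

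The documents give no PHQ cut-point for depression. The only PHQ threshold, in Section 7.2.1, concerns the single suicidal-ideation item. They also give no expected share of patients above the cut, no score distribution, no power for any interaction, and no continuous analysis of these moderators.

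**The concern.** A yes/no split treats all patients on one side of the cut as identical, and treats patients just either side of it as different. If the benefit of the app changes gradually with depression severity, the split version of the interaction test has less chance of showing it, and the answer depends on where the cut falls. With no cut-point on record, that choice is still open.

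Section 8.3 gives these analyses a practical use: finding groups who gain more or less from the app, to shape later implementation. The trial was sized for the main effect only, so the interaction tests have little information to spare. Elsewhere the same section keeps comparable measures continuous: K10, CSS, SCS and craving as mediators, and days of opioid and other substance use as outcomes. It gives no reason for handling the baseline moderators differently.

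**Working it through.** **1. The plan's own figure (Section 8.2).** The plan says "a sample size of 100 patients per treatment group (total N = 200) is selected", for 80% power at two-sided 5% with 40% against 59.7% retained. With mean proportion 0.4985:

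n per arm = [1.96·√(2·0.4985·0.5015) + 0.8416·√(0.40·0.60 + 0.597·0.403)]² / 0.197² = (1.386 + 0.583)² / 0.0388 ≈ 99.9, so 100.

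Power at 100 per arm is 80.03%, and the odds ratio is (0.597/0.403)/(0.4/0.6) = 2.22. Both reproduce. The plan has no figure to reproduce for moderator tests.

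**2. Information kept after a split.** Assume a normal score and an interaction linear in the log-odds. With a share p above the cut c, the fraction kept is the squared correlation of indicator and score, φ(c)² / [p(1−p)]:

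- p = 0.50: 0.3989² / 0.25 = 0.64, a loss of 36%; 200 patients carry the information of about 127.
- p = 0.30: 0.3477² / 0.21 = 0.58, a loss of 42%; about 115 patients.
- p = 0.20: 0.2800² / 0.16 = 0.49, a loss of 51%; about 98 patients.

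An interaction that the continuous score would detect with 80% power then has power Φ[(1.96 + 0.8416)·√kept − 1.96]. This is about 61% at 50/50 and 50% at 20/80.

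**3. Simulated power at N = 200.** The model was logit(retention) = logit(0.40) + A·ln(2.22) + A·slope·x. Here A is 1 in the app arm and 0 otherwise, and x is a standard normal score. There were 100 patients per arm, a Wald test of the interaction at 5%, and 1,500 to 2,000 trials per setting. The slope is an assumption. Figures are rounded, and ranges cover repeated runs.

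| Slope per SD | Continuous score | Split, 20% to 50% above the cut |
|---|---|---|
| 0.8 | about 73% | about 36% to 55% |
| 0.6 | 52% | 25% to 36% |
| 0.4 | 26-28% | 14% to 19% |

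**4. Departure from normality.** For illustrative right-skewed scores (means 8, 10 and 12, SD 6, cuts from 8 to 15), the loss by squared correlation was about 33-58%. The order of magnitude for a PHQ-type score does not hinge on exact normality, but it does hinge on linearity.

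**5. Departure from linearity.** If benefit changes in a step at the cut, the ranking reverses. With a step of 0.8 per SD of the indicator, power was 55%, 70% and 76% for the binary form at 20%, 30% and 50% above the cut. For the linear score it was 33%, 46% and 57%.

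**6. Alcohol and drug use.** Days of use probably pile up at zero (an assumption), so the formula in step 2 does not apply. With 50-90% of patients at zero and various spreads among users, the loss by squared correlation ran from about 5% to 60%. In logistic interaction tests at N = 200, with days spread evenly among users, it was 34%, 20% and about 0% for 50%, 30% and 15% users. The documents give nothing to choose between these.

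**The case against.** The binary form fits the stated aim. Section 7.2.1 presents the PHQ as a diagnostic screen, and Section 8.3 wants treatment effects by usable subgroup whatever the interaction test shows, so the power of that test is not the only criterion. The analyses are openly exploratory. A linear score also carries its own assumption and is the weaker choice if moderation is a step at the diagnostic threshold. These points stand, and they are reasons to keep the yes/no estimates.

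The power loss at a slope of 0.8 is also the favourable end for the continuous score. That slope is as large as the whole planned effect (ln 2.22 = 0.80). It implies odds ratios of 2.22·e^−0.8 ≈ 1.0 at one SD below the mean score and 2.22·e^0.8 ≈ 4.9 at one SD above. At half that slope the gain is only about 7 to 14 points (26−19 to 28−14), and both versions usually miss the effect. This stands too, and is why both slopes are shown.

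A reader might also infer that this trial will discard 36-51% of its moderator information, and that the figure covers alcohol and drug use as well. The documents support neither. The percentages need a distribution, a shape and a share above the cut that are not given. For substance use, the split lies at a natural zero, where none against any is a substantive distinction.

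None of this answers the missing cut-point or the absence of any analysis of the collected score.

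**Conclusion.** The point holds as a minor improvement to an exploratory analysis. The missing cut-point and the lack of a continuous PHQ analysis can be read directly from Section 8.3 and need no assumption. The size of the loss is conditional: 36% of the interaction information at a 50/50 cut and 51% at 20/80, if the score is roughly normal and moderation is linear in the log-odds. The power cost depends heavily on the assumed slope, and the advantage reverses under a step at the cut. No percentage should be claimed for alcohol and drug use. Nothing here bears on the primary test, and the sample size reproduces.

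**What to change.** In Section 8.3:

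- Add treatment by continuous baseline PHQ score as the exploratory moderation test for depression, linear in the score, with a spline as a check of shape.
- Report the treatment effect with its 95% confidence interval at score values named in advance.
- State the PHQ cut-point before the data are seen.
- Keep the yes/no subgroup estimates beside the continuous result, since they serve the subgroup aim and are the better form if moderation is a step.
- Optionally, add baseline Timeline Follow-Back days of use as a supplementary moderator next to the any/none indicators.

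The cost is a few lines of plan text and code. No new data are needed, and the moderation equation already accepts a continuous moderator. The downside is a shape assumption and one or a few extra exploratory tests.
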